### 4.3. Selection of Study Population

This study will enroll healthy volunteers 18 to 65 years old. Participants will be enrolled in an equitable way with best practices to balance sex and age applied to the study population. Recruitment of not more than 5/3 or less than 3/5 Male-to-Female (M/F) ratio for each experimental group and not more than 3/1 or less than 1/3 M/F ratio for each placebo group may be obtained. Should a participant replacement be necessary within a

cohort, the replacement participant will receive the same treatment, and attempts will be made to be of the same gender as the withdrawn participant. Participant Inclusion and Exclusion Criteria must be confirmed by a study clinician licensed to make medical diagnoses. No exemptions are granted on Participant Inclusion/Exclusion Criteria in DMID-sponsored studies.

#### 4.3.1. Inclusion Criteria

In order to be eligible to participate in this study, an individual must meet all of the following criteria:

1. Provision of signed and dated informed consent form.
2. Able to understand and willing to be available for all study visits and comply with all study procedures including Lifestyle Considerations (see Protocol v4.0 Section 5.4) throughout the study.
3. Male and Female individuals, age 18-65 inclusive at time of enrollment.
4. Good general health by medical history (MH), physical examination (PE), and vital signs (VS), clinical laboratory tests and ECG within normal reference range.
  - Note 1: *Lab exceptions include: lab test values that are within Grade 1 range per the Toxicity Table (Table 8) are acceptable if not considered to be clinically significant by the investigator (PI, sub-investigator, or authorized clinician), with the exception of liver function tests (LFT) (transaminases alanine aminotransferase (ALT), aspartate aminotransferase (AST), alkaline phosphatase (AP), total and direct bilirubin, serum creatinine, estimated glomerular filtration rate (eGFR) per the CKD-EPI formula, and urine protein, which must be within the laboratory normal reference range.*
  - Note 2: *Screening laboratory values that fall outside the laboratory normal reference ranges and the ranges are not listed within the Toxicity Table (Table 8) (e.g., decrease activated partial thromboplastin time [aPTT]) that are deemed Not Clinically Significant by the PI will be acceptable.*
5. Ability to take oral medication and be willing to adhere to the dosing regimen.
6. Women of childbearing potential must have practiced or use true abstinence or use at least one acceptable primary form of contraception for specified periods before, during and after dosing.
  - Note 1: *Not of childbearing potential – post-menopausal females (defined as having a history of amenorrhea for at least one year) or a documented status as being surgically sterile (hysterectomy, bilateral oophorectomy, salpingectomy, tubal ligation, or Essure® placement with a history of documented radiological confirmation test at least 90 days after the procedure).*
  - Note 2: *True abstinence is 100% of the time without sexual intercourse (the male's penis enters the female's vagina). Periodic abstinence [e.g., calendar, ovulation, symptothermal, post-ovulation methods] and withdrawal are not acceptable methods of contraception).*
  - Note 3: *Acceptable forms of primary contraception include a monogamous relationship with a vasectomized partner who has been vasectomized for 180 days or more before the participant receiving the study product, tubal ligation, non-hormonal intrauterine device, and if in a monogamous relationship with a male partner who uses a barrier method without spermicide.*
  - Note 4: *Specified periods include at least 30 days prior to screening, during the period between screening and completion of dosing, and until at least 30 days following receipt of the last dose of study product.*
7. Women of childbearing potential must have a negative serum β-human chorionic gonadotropin (HCG) pregnancy test at screening and a negative urine HCG pregnancy test at check-in (Day-1) within 24 hours before receiving the initial study product.

---

8. Male participants receiving the study product must use acceptable contraception and refrain from donating sperm from the day of first dose until 30 days after the last dose or be vasectomized.
  - *Note 1: Acceptable contraception includes abstinence from intercourse with a female of childbearing potential or use of a male condom without spermicide when engaging in any activity that allows for the passage of ejaculate to a female during the intervention period and for at least 30 days after ending study dosing, or surgical sterilization for 180 days or more.*
9. Willing to avoid excessive physical exercise starting within 48 h prior to dosing and until discharge from the CTU on Day 9.
10. No history of acute febrile or infectious illness for at least 7 days prior to the administration of study drug.

#### 4.3.2. Exclusion Criteria

An individual who meets any of the following criteria will be excluded from participation in this study:

1. Pregnant or lactating.
2. History of any chronic disease that may increase risk to subject or interfere with endpoint assessment.:
  - *Note 1: With the exception of stable chronic medical conditions that do not require prescribed oral or injectable medications (e.g., Type 2 diabetes managed by diet only).*
3. History of bradycardia, orthostatic hypotension or orthostatic tachycardia, Long COVID or history of dysautonomia.
  - *Note 1: Exception is sinus bradycardia (HR <60 bpm) in healthy participants (e.g., conditioned athletes) could be enrolled per investigator's clinical judgement.*
4. Known history of a clinically significant food or drug allergy/hypersensitivity including known allergy/hypersensitivity to ingredients of the study drug or placebo.
5. Current seasonal allergies with ongoing symptoms for more than a week prior to dosing requiring glucocorticoids and/or frequent use of antihistamines for treatment.
6. History of any clinically significant disease or disorder, medical/surgical procedure, or trauma within 4 weeks prior to initiation of administration of study product(s).
7. History of any psychiatric condition that has required hospitalization in the last 12 months or subject is considered psychologically unstable by the investigator.
8. History of any substance use disorder or positive urine drug screening (UDS) test for illicit substances listed in Protocol v4.0 Section 8.1 at Screening or Check-in (Day -1).
  - *Note 1: Any approved medical use of amphetamines, barbiturates, benzodiazepines, cannabis, tricyclic antidepressants and opiates will not be acceptable.*
9. History of alcoholism or of binge or heavy alcohol drinking at any time in the 6 months before study product administration or positive urine alcohol test at Screening or Check-in (Day -1).
  - *Note 1: Binge drinking is defined as 5 or more drinks during a single occasion if male, or 4 or more if female.*
  - *Note 2: Heavy drinking of alcohol is defined as consumption of more than 14 drinks of alcohol per week if male, or more than 7 drinks if female.*
10. History of  $\geq 10$  pack-years of nicotine product consumption in the 5-year period before screening, or positive urine cotinine screen at Check-in (Day -1).

- *Note 1: Nicotine products include cigarettes, e-cigarettes, pipe, cigar, chewing tobacco, nicotine patch.*
- *Note 2: Positive urine cotinine at Screening is allowed if negative at Check-in (Day -1).*

11. Body mass index (BMI)  $\leq 18 \text{ kg/m}^2$  or  $\geq 32 \text{ kg/m}^2$ , or weight  $\leq 100 \text{ lbs}$  at Screening.
12. Prior exposure to SLV213 or K777 or K11777.
13. Use of any prohibited prescription or non-prescription medication within 14 days or 5 half-lives of the drug, whichever is longer, prior to study Check-in. (See [Section 4.4.7](#))
14. Use of any investigational drug product within 30 days or 5 half-lives (whichever is longer) before investigational product administration in this study.
15. Planned participation in a clinical research study that requires treatment with a study drug, blood draws or other invasive assessments during the study period (screening until final visit).
16. Blood or plasma donation of 500 mL within 3 months or more than 100 mL within 30 days before signing informed consent or planned donation prior to completion of this trial.
17. Positive viral serology tests for Human Immunodeficiency Virus (HIV), hepatitis B virus, or hepatitis C virus (HCV) at screening (See Protocol v4.0 Section 8.1) with one exception:
  - *Note 1: Viral serology tests include HIV 1 and HIV 2 antibodies, Hepatitis B virus surface antigen (HBsAg), and HCV antibodies.*
  - *Note 2: Do not exclude participants with HCV antibodies who have been successfully treated for Hepatitis C, do not take any treatment medications currently, do not use prohibited medications, have normal transaminases and are generally healthy.*
18. Positive SARS-CoV-2 (COVID-19) molecular diagnostic test (Cue CareTM test) at Check-in (Day -1).

#### **4.3.2.1. Exclusion of Specific Populations**

Because the effects on the fetus are not known, pregnant women will not be eligible for the trial. Women of childbearing potential must utilize a highly effective method of contraception and will be required to have a negative urine pregnancy test on Check-in (Day -1) (within 24 h prior to initiation of study drug administration).

Children will not be included in this trial as presently there are no safety or efficacy data in adults. Should the outcome of this trial be deemed acceptable, additional trials may be initiated, including those in other populations.

### **4.4. Treatments**

#### **4.4.1. Treatments Administered**

##### **Study intervention:**

- SLV213 capsules containing 100 mg of a refined powder of drug substance K777 hydrochloride.
- Matching placebo capsules containing 62.5 mg microcrystalline celluloid.

Each participant will be randomly assigned to receive SLV213 or placebo (SLV213:placebo ratio 2:1) by mouth as follows: 4 capsules Q12h in Cohort 1, 6 capsules Q12h in Cohort 2, and 8 capsules Q12h in

Cohort 3. The SLV213 dose will be 400 mg Q12h, 600 mg Q12h and 800 mg Q12h for participants in Cohorts 1, 2 and 3, respectively, for 7 days.

This study was terminated after Cohort 1 and will not proceed with sequential cohorts.

#### 4.4.2. Identity of Investigational Product(s)

In this SAP, the term “study drug” refers to all or any of the drugs defined below:

##### **Product 1: SLV213 in 100 mg capsules**

SLV213 drug substance (K777) is 4-methylpiperazine-1-carboxylic acid [1-(3-benzenesulfonyl-1-phenethyl-allylcarbamoyl)-2-phenylethyl]-amid) as hydrochloride salt. SLV213 is a white to tan powder of the drug substance without excipients or stabilizer that will be packed into Swedish orange opaque size 1 capsules. It is an investigational drug product that is being used to accordance with approved labeling.

##### **Drug Substance Characteristics**

Molecular weight	611.19 (574.73 free base)
Molecular formula	$C_{32}H_{39}ClN_4O_4S$
Calculated pKa	7.02

##### **Product 2: Matched Placebo**

Placebo for SLV213 drug product is manufactured as microcrystalline cellulose in a size 1 orange hard gelatin capsule.

#### 4.4.3. Method of Assigning Participants to Treatment Groups (Randomization)

Participants in each cohort will be randomized 2:1 to drug versus placebo before dosing on Day 1 and receive assigned treatment at each dose.

#### 4.4.4. Selection of Doses in the Study

Selva has conducted a Phase 1 randomized double-blind placebo-controlled SAD study in healthy volunteers to evaluate the safety, tolerability, and PK of SLV213 following oral administration (Study SLV213-01). Following randomization, 5 cohorts of 8 participants each (6 active, 2 placebo) received a single dose of the active compound SLV213 or placebo at 50 mg, 100 mg, 200 mg, 400 mg, or 800 mg PO daily (QD). A SRC evaluated the blinded results of each successive cohort before proceeding to dose the next cohort. Although a clinically significant episode of orthostatic hypotension was observed 30 minutes (min) after dosing in one participant at the 200 mg dose level, this was not seen in this participant at subsequent time points, nor in any other participant at the 400 mg or 800 mg dose levels. The SRC therefore concluded that no dose limiting toxicity (DLT) had been seen at any of the dose levels. PK analyses demonstrated dose dependent  $C_{max}$  and AUC. Preliminary modeling of 400 mg and 800 mg BID using predicted blood levels showed exposures comparable to concentrations measured in preclinical efficacy models. It is therefore concluded that 400 mg Q12h, 600 mg Q12h and 800 mg Q12h dosing should be well tolerated. Further description of the results of the SLV213-01 study is provided in the investigator's brochure (IB).

This study was terminated after Cohort 1 (400 mg) and will not proceed with sequential cohorts (600 mg and 800 mg).

#### **4.4.5. Selection and Timing of Dose for Each Participant**

Participants will take their study drug prior to morning and evening meals in the fasted state with at least 240 mL (8 fluid ounces) or more of tap or bottled water under the supervision of the site staff. Participants will not be re-dosed outside of the standard schedule of events. A list of study products by cohort is available in **Table 1**.

Dose modifications are not planned unless mandated by the SMC.

#### **4.4.6. Blinding**

The study will be double-blinded, placebo-controlled. Placebo capsules are made to mimic study drug to avoid unblinding. Study drug and placebo are in matched bottles with matched capsule sizes. Administration of drug and placebo is controlled by the CTU as designated on the Delegation of Authority Log.

The investigational drug blind shall not be broken by the investigator unless information concerning the investigational drug is essential for the medical treatment of the participant. If possible, the DMID Medical monitor should be contacted before the investigational drug blind is broken to discuss the need for unblinding.

For unblinding a participant, the investigational drug blind can be obtained by contacting the dispensing pharmacist. The emergency unblinding information will be obtained from the statistical and data coordinating center (SDCC). The sponsor (investigational new drug [IND] holder) must be notified as soon as possible if the investigational drug blind is broken. The date, time, and reason the blind is broken must be recorded in the source documents. Details will be presented in the study-specific manual of procedures (MOP).

#### **4.4.7. Prior and Concomitant Therapy**

For this protocol, a prescription medication is defined as a medication that can be prescribed only by a properly authorized/licensed clinician. Medications to be reported in the Case Report Form (CRF) are concomitant prescription medications, and supplements.

Information about prior medications, including hormonal contraceptives, taken by the participant in the 30 days prior to initiation of dosing with study product(s) will be recorded on the appropriate CRF.

Concomitant medications include all medications (prescription and over-the-counter [OTC] medications, supplements, and vaccines), except study products, taken by the participant from the time of the first dose of study product(s) to the end of the study. At each study visit following dosing, including telephone calls, participants will be queried about new ConMeds and changes to existing medications. The following medications are prohibited during the study:

- No medications are allowed after enrollment until completion of all study assessments with the exception of up to 1,000 mg acetaminophen daily for up to 3 days for the relief of common, temporary symptoms (headache, musculoskeletal pain, etc.) if approved by the site PI or authorized clinician.
- Any medications known to be strongly metabolized by CYP3A4 or CYP2D6, or strongly inhibit or induce these enzymes might interfere with the evaluation of the investigational product and should not be used by the participant for 14 days or 5 half-lives of the drug, whichever is longer, prior to and during the study. (See Protocol v4.0 Appendix C for a partial list).

- Participant should refrain from OTC supplements, such as vitamins and herbal supplements (e.g., Saint John's Wort), for 14 days or 5 half-lives of the supplement, whichever is longer, prior to and for the duration of the trial.

In the event medical conditions dictate the use of medications during the in-patient period, appropriate treatment may be prescribed by authorized/licensed clinician. For events during the out-patient period, participants are encouraged to notify the investigator or, if they seek care by their personal healthcare provider, to comply with the course of therapy as prescribed and inform the study investigator as soon as practical.

Any drug or vaccine used or received by the participant during the trial should be recorded on the appropriate CRF.

For additional lifestyle restrictions, see Protocol v4.0 Section 5.4.

#### 4.4.8. Treatment Compliance

Participants will be directly observed at the time of dosing by a member of the clinical research team who is licensed and authorized to administer the study product (PI, sub-investigator or licensed clinician listed in Form 1572, or staff listed in the study Delegation of Authority Log). Each dose of study product will be administered by a member of the clinical research team that is delegated to administer the study product.

Study product administration date and time will be documented on site source document and recorded on the appropriate eCRF.

### 4.5. Safety and Pharmacokinetic Variables

The following section describes the safety and PK variables of the study. As this study is a Phase 1 clinical trial in healthy adult participants, there will be no assessment of drug efficacy.

#### 4.5.1. Safety Variables

Venipuncture schedule and blood volumes are shown in schedule of assessments ([Table 3](#)). The following safety endpoints will be assessed:

- Chemistry (CHEM), Hematology (HEM), Coagulation (COAG), and Urinalysis (UA) clinical laboratory result safety parameters will be collected at Screening, Day -1, and prior to the morning dose on Days 2, 4, and 6, and on Day 8 or at early termination.
  - CHEM parameters: Electrolytes (sodium, potassium, total carbon dioxide [CO2]), calcium, chloride, creatinine, blood urea nitrogen (BUN), fasting glucose, total protein, albumin, total bilirubin, alanine aminotransferase (ALT), aspartate aminotransferase (AST), alkaline phosphatase (ALP), amylase, lipase, magnesium, and inorganic phosphorus.
    - Note 1: Estimate glomerular flow rate (eGFR) and direct bilirubin will be collected but not graded.
  - HEM parameters: Hemoglobin, platelets, white blood cells (WBC), neutrophils, lymphocytes, monocytes, basophils, and eosinophils.
    - Note 1: Red blood cells (RBC) will be collected but not graded.
  - COAG parameters: Prothrombin time and activated partial thromboplastin time (aPTT).

- Note 1: Prothrombin time international normalized rate (PT INR) will be collected but not graded.
- UA parameters: Nitrite, urine protein, and urine glucose via dipstick.
  - Note 1: pH, specific gravity, bilirubin, and occult blood will be collected but not graded.
  - Note 2: If urine dipstick is abnormal for blood, protein, glucose, and nitrites, urine microscopy will be performed (for WBC, RBC, and bacteria), and the results will supersede those of the dipstick UA.
- Vital signs (VS) will be collected at Screening, Day -1, within 30 minutes before and 2 hours ( $\pm$  10 minutes) after each dose on Day 1 through Day 7, and the mornings of Days 8 and 9.
  - Supine VS parameters: Body temperature (oral), systolic blood pressure (SBP), diastolic BP (DBP), pulse, and respiratory rate.
    - Note 1: BP will be taken after at least 5 minutes of resting.
  - Orthostatic VS parameters: SBP, DBP, and pulse
    - Note 1: Orthostatic parameters will be measured 1 minute  $\pm$  15 seconds and 3 minutes  $\pm$  15 seconds after standing.
- Electrocardiogram (ECG) results will be collected at Screening, Day -1, and prior to the morning dose on Day 4, and Day 8 (before 12h PK timepoint after Day 7 evening dose) or at early termination.
  - ECG parameters: PR interval, QRS interval, QT interval, QT interval corrected for heart rate using Fridericia's formula (QTcF correction), RR interval, and ventricular rate.

Incidence, relatedness, and severity of TEAEs and SAEs will be recorded from the time of dosing to the final visit on the appropriate eCRF. All AEs will be graded for severity and relationship to the study product by a trained and qualified member of the study team. All AEs and SAEs will be considered unsolicited events.

Abnormal clinical assessments should be submitted in the appropriate AE form. If a participant had an event with graded severity after enrollment on Day -1 but before dosing on Day 1, then the event will be reported in an updated medical history (MH) form and will be considered an AE only if it increases in severity grade after dosing.

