8.1.1 Clinical Procedures and Evaluations

- **Demographics:** Demographic information (date of birth, gender, ethnicity, and race) will be recorded on the subject's source documents and eCRF at Screening Visit. Name, address, phone number, and emergency contact information will be documented in the source documents only.
- **Eligibility Review:** A review of study inclusion and exclusion criteria will be completed within 28 days before study drug dosing at the Screening and Check-in (Day -1) visits. Confirmation of eligibility for dosing will be performed before dosing on Day 1.

Screening failures and the reason for failure to meet the study eligibility requirements will be documented in source documents and eCRFs.

- **Medical History (MH):** A review of pertinent MH that may impact study participation will be obtained by direct interview of the subject. The MH will capture current disease processes, past disease processes, history of hospitalization, and history of surgery. Participants will be queried regarding a history of significant medical disorders of the head, eyes, ears, nose, throat (HEENT), mouth, skin, the cardiovascular, respiratory, gastrointestinal, renal, urological, nervous, hematological, lymphatic, endocrine, musculoskeletal and genital/reproductive systems. A history of allergies including allergies to medications, medication history, and history of substance and alcohol abuse will be obtained.

Participants will be queried about a history of orthostatic hypotension, any symptoms associated with position change, syncope or near syncope (i.e., dizziness, fainting), and symptoms related to transition from lying down to standing up (such as fast heart rate, dizziness, or fainting).

The MH will be obtained at Screening Visit and updated on Day -1 (Check-in) and before dosing on Day 1. After start of study drug dosing, any worsening of pre-dosing MH or new symptoms will be evaluated and reported as TEAEs.

- **Concomitant Medications (ConMeds):** Medication history will include prescription medication, including contraceptives, and non-prescription drugs, vitamins, supplements and herbal medication, and recent vaccinations including for COVID-19 used in the recent past, and include medications that are prohibited prior to dosing. (See [Section 6.5](#)).

Medications history will be obtained at Screening, Check-in (Day-1) and updated prior to dosing on Day 1. Medications taken prior to dosing will be recorded as “Prior Medications”.

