8.3.1 Clinical Procedures and Evaluations

- **Medical History (MH):** After start of study drug dosing, any worsening of pre-dosing MH or new symptoms, including orthostatic symptoms, will be evaluated and reported as TEAEs.

An interim MH will be obtained by interview of participants for evaluation of TEAEs from Day 1 to the last study visit, and any changes since the previous clinic visit or telephone call after discharge from the CTU will be noted. The interim MH should include an assessment for new medical conditions and symptoms suggestive of Medically- Attended AEs (MAAEs) (see [Section 8.5.3](#)) and protocol specified adverse events of special interest (AESIs) (See [Section 8.5.9](#)).

- **Assessment of TEAEs and SAEs:** Unsolicited AEs will be evaluated from the time of initial dosing to the last study visit (Day 28 ±2 days) (See [Section 8.5](#)). During the Inpatient treatment period, (Day 1 to Day 9), the participants will be monitored as inpatients and complete scheduled assessments. Following discharge on Day 9, CTU staff will contact the participants by phone on Days 15 (±2 days), 21(±2 days), and 28 (±2 days) and inquire about their well-being, the emergence of any AEs since the last visit and the use of any ConMeds. Based on the information collected, participants will be asked to return to the CTU for evaluation.
- **Concomitant Medications (ConMeds):** No medications are allowed after enrollment until completion of all study assessments with the exception of up to 1,000 mg acetaminophen daily for up to 3 days for the relief of common, temporary symptoms (headache, musculoskeletal pain, etc.) if approved by the site PI or authorized clinician. (See [Section 6.5](#) for prohibited medications during the study).
- **Physical Examination (PE):**
 - **A symptom-directed (focused) PE** may be performed for evaluation of new symptoms reported from the time of admission on Day -1 to before the first dose on Day 1 and assessment of TEAEs at any time after dosing on Day 1 to the last study visit, focusing on orthostatic vital signs and symptoms.
 - **A complete PE** will be performed on Day 9 prior to discharge from the CTU. (See [Section 8.1.1](#))

Any abnormal finding on a PE performed after dosing on Day 1 must be assessed as Not Clinically Significant (NCS) or Clinically Significant (CS) by the investigator (PI, sub-

investigator, or authorized clinician) listed on Form FDA 1572 and recorded in the source document and eCRF.

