8.5 Adverse Events and Serious Adverse Events

8.5.1 Definition of Adverse Events (AE)

An AE means any untoward medical occurrence associated with the use of an intervention in humans, whether or not considered intervention-related (21 CFR 312.32 (a)). An AE can therefore be any unfavorable and unintended sign (including an abnormal laboratory finding), symptom, or disease temporally associated with the use of medicinal (investigational) product.

An AE is the development of an undesirable medical condition or the deterioration of a pre-existing medical condition following or during exposure to a pharmaceutical product, whether or not considered causally related to the product. In clinical studies, an AE can include an undesirable medical condition occurring at any time, including baseline or washout periods, even if no study treatment has been administered.

Symptoms that increase in severity or frequency will be considered as AE's and processed accordingly.

Any medical condition that is present at the time the participant is screened will be considered as baseline and not reported as an AE. However, if the severity (i.e., grade) of any pre-existing medical condition increases, it should be recorded as an AE.

Adverse events can be further divided into solicited AEs and unsolicited AEs:

- Solicited AEs are those for which the study team will specifically query the participant whether they occurred. **Solicited AEs are not collected in this study.**
- Unsolicited events are all AEs spontaneously reported by the participant and/or in response to an open question from study personnel or revealed by observation, PE or other procedures. **All AEs collected in this study are unsolicited events.**

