### **3.1. Study Definitions and Derived Variables**

#### **Adverse Events**

All AEs collected in this study will be considered unsolicited. Treatment-emergent AEs (TEAEs) are defined as AEs that occur or worsen after beginning study drug administration.

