**Table 6: Adverse Event Grading Scale**

Parameter	Grade 1/Mild	Grade 2/Moderate	Grade 3/Severe	Grade 4/ Potentially Life-Threatening
Clinical adverse event NOT identified elsewhere in the grading table	Mild symptoms causing no or minimal interference with usual social & functional activities with intervention not indicated	Moderate symptoms causing greater than minimal interference with usual social & functional activities with intervention indicated	Severe symptoms causing inability to perform usual social & functional activities with intervention or hospitalization indicated	Potentially life-threatening symptoms causing inability to perform basic self-care functions with intervention indicated to prevent permanent impairment, persistent disability, or death

The functional table below should be used to grade the severity of an AE that is not specifically identified in the grading table. In addition, all deaths related to an AE are to be classified as Grade 5.

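### SAP 4.5.1 counts a symptom that arose between check-in and first dose as an AE only if its grade rises, whereas protocol 8.5.1 also counts a rise in frequency

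*SAP*

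**What the plan says.** SAP section 4.5.1 sets a rule for a narrow window: "If a participant had an event with graded severity after enrollment on Day -1 but before dosing on Day 1". Such an event goes on an updated medical history form and "will be considered an AE only if it increases in severity grade after dosing". The clause makes no distinction between symptoms, clinical events and laboratory findings.

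The protocol's AE definition (section 8.5.1) states: "Symptoms that increase in severity or frequency will be considered as AE's and processed accordingly". For the period after dosing starts, section 8.1.1 says that "any worsening of pre-dosing MH or new symptoms will be evaluated and reported as TEAEs", and section 8.3.1 repeats this for the in-patient period and names orthostatic symptoms.

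Elsewhere the SAP uses no grade threshold for TEAEs. Section 3.1 describes them as "defined as AEs that occur or worsen after beginning study drug administration", and section 9.3 treats every unsolicited AE collected once the first dose has been received as a TEAE. Section 15 lists one change from protocol version 4.0, the stop after Cohort 1.

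**The concern.** The words 'only if' in SAP 4.5.1 shut out every route to AE status except a higher grade. The protocol gives a second route for symptoms, a higher frequency, and a symptom can take that route without any change of grade.

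The primary safety endpoint is the type, incidence, severity and relatedness of TEAEs, and one primary tolerability item is the number of participants with at least one TEAE. If the SAP clause is followed to the letter, a symptom that was present once at check-in and became frequent on drug is missing from these counts. It would also be missing from the preferred-term rows and event counts of SAP Table 24, even for a participant who has other TEAEs. Protocol 8.5.6 asks for the onset and duration of each episode of an intermittent AE, so frequency was meant to be captured.

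**Working it through.** The plan gives no figure to reproduce here. The check is a comparison of rules, followed by a scale calculation.

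**1. What each rule says about a symptom that began on Day -1, stays at the same grade and becomes more frequent on drug.**

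| Place | Applies to | Makes it an AE or TEAE | Result for this symptom |
|---|---|---|---|
| SAP 4.5.1 | Graded events from Day -1 enrollment to first dose | Rise in grade only | Not an AE |
| Protocol 8.5.1, sentence on symptoms | Symptoms | Rise in severity or frequency | AE |
| Protocol 8.5.1, sentence on grade | Conditions present at screening | Rise in grade | Outside its scope |
| Protocol 8.5.6 | Laboratory values | Worse severity only | Outside its scope |
| Protocol 8.1.1 and 8.3.1 | Pre-dosing history; new symptoms | Any worsening; any new symptom | Depends on how worsening is read |
| SAP 3.1 | AEs | Occurrence or worsening | Depends on how worsening is read |
| SAP 9.3 | Unsolicited AEs collected after first dose | Being collected | TEAE if the site recorded it |

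The direct conflict is between the first two rows. The protocol's two severity-only sentences do not reach this event: one concerns conditions present at screening, the other laboratory values.

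**2. Whether grade could stand in for frequency.** SAP Table 6 grades by interference with activity. Grade 1 is "Mild symptoms causing no or minimal interference with usual social & functional activities with intervention not indicated". One mild headache on Day -1 that turns into daily mild headaches on drug can therefore remain Grade 1. It is an AE under protocol 8.5.1 and not under SAP 4.5.1.

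**3. Weight of one participant.** Inputs: Cohort 1 was planned as 8 SLV213 and 4 placebo (SAP 2.1). Four replacements were added (SAP 6.2) and belong to the Safety Population if dosed (SAP 6.3.3); their arms are not stated. So n lies between 8 and 8 + 4 = 12 on SLV213, and between 4 and 4 + 4 = 8 on placebo. The shift in the percentage with at least one TEAE, if that participant has no other TEAE, is 100/n:

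- SLV213: 100/8 = 12.5 points; 100/12 = 8.3 points.
- Placebo: 100/4 = 25 points; 100/8 = 12.5 points.

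SAP Table 4 gives 6 for the 400 mg group, which disagrees with 8; 100/6 = 16.7 points lies inside the overall range of 8.3 to 25.

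With the exact Clopper-Pearson interval of SAP 9.3, and assuming that this is the only SLV213 participant with a TEAE:

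- n = 8: 1/8 = 12.5% (95% CI 0.3 to 52.7) becomes 0/8 = 0% (0 to 36.9).
- n = 12: 1/12 = 8.3% (0.2 to 38.5) becomes 0/12 = 0% (0 to 26.5).

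These counts are assumed and show scale only.

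**The case against.** The strongest reply is that nothing in the SAP deletes an AE. The investigator identifies and records AEs under the protocol, SAP 9.3 counts what was collected, and 4.5.1 only describes how variables are recorded. This stands in part: if the site followed the protocol, the event is in the AE data and 9.3 counts it. But one SAP then gives two answers for the same event, and the stricter one is worded as exclusive.

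A second reply is that 'worsening' is commonly defined as a rise in grade, so SAP 3.1 and protocol 8.1.1 and 8.3.1 do not contradict 4.5.1. That is fair. The point rests on the word 'frequency' in protocol 8.5.1, not on those sections.

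A third is that an event the site never recorded will not appear because a SAP sentence changes. This also stands, and it is why the check has to go to source records as well as AE records.

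Some stronger readings are tempting but not supported:

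- *That the clause could have hidden a halting trigger.* Halting is governed by protocol 7.1 and judged on reported events by the safety committees. The SAP itself reports that the halt had already happened.
- *That events which resolved before dosing and then returned are lost.* Neither document says that such an event is the same event. It can be read as a new symptom under protocol 8.1.1 and 8.3.1 and as an occurrence under SAP 3.1. The SAP is silent here, which is a reason to state a rule.
- *That the TEAE rate is biased more in one arm.* The documents give no data on these events in either arm.

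**Conclusion.** The conflict on frequency is real, is not declared in SAP section 15, and should be corrected. Under the literal SAP rule, a symptom that stays at its grade but becomes more frequent after dosing drops out of a primary count that the protocol includes.

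The practical effect is probably small. The window runs only from enrollment on Day -1 to the first dose, and the number of such events is not given. A reader might take the range of 8.3 to 25 points as an expected error; it is only the weight of one participant. It assumes that the event was not recorded as an AE, that it was that participant's only TEAE, and that the arm sizes lie in the ranges above.

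The conclusion is limited to symptoms and clinical events. For laboratory values, protocol 8.5.6 itself uses severity alone, so the SAP rule is broadly consistent there.

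**What to change.** In SAP 4.5.1:

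- For symptoms and clinical events, reword the clause so that a pre-dose event becomes an AE *if either its severity grade or its frequency rises after dosing*.
- Keep the severity-only rule for laboratory values and refer to protocol 8.5.6.
- Add that an event which resolved before the first dose and reappears after dosing is a new event, and so a TEAE under SAP 3.1.

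Then compare the medical history entries made on Day -1 and before dosing on Day 1 with post-dose source notes and AE records, so that a more frequent symptom left only in the history is found.

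If the narrower rule was intended, list it in section 15 with a reason. SAP section 15 allows an addendum before final data lock but no amendment after it; if lock has passed, describe the handling in the clinical study report.

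The cost is a few sentences and a review of what should be a small number of history entries in one cohort. The TEAE count may rise slightly.
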